## Introduction

Temporomandibular disorders (TMDs) are the most common non dental orofacial pain influencing tempomandibular joint (TMJs), orofacial muscles, or both.(1)

The Most common symptom is pain, which is generally localized to the masticatory muscles, pre-auricular area and temporomandibular joint.(1,2)

The significant clinical signs and symptoms of TMDs are muscle/TMJ pain, TMJ sounds, limitation, deviation, or deflection of mandibular movements(3)

The prevalence of TMDs is higher among people in the 25-45 age range, women are more affected, and psychosocial problems cause higher prevalence and greater intensity of TMD symptoms.(3)

Surgical approaches are only indicated in patients without any improvement following conservative treatments after at least six months and those with severe disability.(3)

IN DENTISTRY, Low-level laser therapy (LLLT), recently named photobiomodulation which has been

Photobiomodulation therapy (PBMT) has an anti-inflammatory effect due to the light absorption in intracellular photo-acceptors and modulation of cell responses. Photo biomodulation therapy emitting infrared spectrum.(4,6) Photobiomodulation therapy (PBMT) increases the blood microcirculation, vascularization, and proliferation of the fibroblasts cells, ATP production, as well as reducing edema and the level of cyclooxygenase-2 (COX2) and prostaglandin E2 (PGE2) as a result of increased lymphatic flow.(4,5)

RECENTLY, Evaluation of the effect of photobiomodulation therapy depend on pain intensity, maximum mouth opening(MMO), lateral movements(LM), protrusive movements(PM), pressure pain threshold, electromyography activity and TMJ sounds in patients with TMDS.(3,4,5)

Photobiomodulation therapy has been used to relieve pain for temporomandibular disorders in combination with conventional therapies such as physiotherapy exercises and occlusal splints. Published outcome data report diode lasers with a wavelength of between 650 and 1000 nm, with fluences of between 1.5 and 140 J/cm^2. Treatments are usually repeated two or three times a week until the symptoms have disappeared.(7)

## Review of literature

Nima Farshidfar in 2023 , Effects of PBMT on the alleviation of pain and improvement in Maximum mouth opening. Using the infrared diode laser with a wavelength ranging between 780-980 nm, an energy density of <100j/cm^2, and an output power of ≤500 mW for at least six sessions of treatment seems to be a promising option for treating mentioned TMDs signs and symptoms.(1)

Ahmed Fadhel Al-Quisi in 2023, Both LED light and LASER therapies could effectively relieve pain associated with myogenic TMD as there were no important differences between their outcomes. However, the biosafety and lower cost of the LED light device compared to the LASER should also be considered. The LED light device used in the current study had a wavelength of 660 nm (red light) with a power of 1.6 Watt, which is equivalent to 1.6 J of work per second. The Diode LASER had the following parameters: wavelength = 810 nm, 2.5 Hz, and power = 1 Watt.(23)

Nahla Mahmoud Awad in 2023, A laser group showed more improvement in the pain and mouth opening measurements infrared lamp therapy. A vicious cycle of pain, muscle spasms, and more pain has been said to be broken by enhancing microcirculation through the utilization of laser therapy. This could improve the supply of oxygen to the cells in low-oxygen environments and aid in getting rid of waste products from cell metabolism. Diode Soft Tissue LASER, , 980 nm, 3.5w CW/6.0w .a 7 W laser beam with a 2.8 cm^2 spot size transmitted radiation continuously at an intensity of 960 nm. Each application lasted 3 minutes (24 s per application point). For ten days, the session was repeated every two days. The laser was applied extra orally to certain points: preauricular, mastoid, angle of the mandible, temporal, and zygomatic.(6)

Mohammed Nadershah in 2020, Photobiomodulation therapy proved to be an effective short-term therapeutic modality for myofascial TMD pain. It is non-invasive, easy to apply with no systemic side effects. Its long-term effect and its effect on different subtypes of TMD need further investigation. Patients with unilateral TMJ and masticatory muscles pain during function were recruited and divided into two groups: a control group that received a sham laser treatment every 48 h for 10 days and a test group that received the same frequency of treatment to deliver a dose of 257 J per treatment and a total dose of 1285 J for the entire treatment. For the test group, a diode laser was applied using the Ezlase 940 device. A 7 W laser beam with a 2.8 cm^2 spot size emitting radiation continuously at a wavelength of 940 nm was applied by the therapist extraorally and at a 2 cm distance from the skin to 5 points at the temporal (center of Temporalis muscle), zygomatic (origin of Masseter muscle), angle of the mandible (insertion of Masseter muscle), pre-auricular, and mastoid areas. Each application lasted 2 min (24 s per application point) so that each patient received approximately 300 J of energy per treatment .(30)

Sabrina Araújo Pinho COSTA in 2017, treatment of masticatory muscles, The photobiomodulation therapy (830 nm) acted effectively on the analgesia of the masticatory muscles in the participants with TMD, based on muscular palpation, but was not effective regarding the criteria for mouth opening range. Further research is needed to evaluate the long-term effects of PBMT (830nm) on the treatment of patients with chronic pain from temporomandibular disorders.(31)

### Aim of the study

To assess the effect of low level laser therapy (LLLT) to relieve pain in myofacial pain syndrome (MPS), caused by fatigue of temporalis and masseter muscles, by using 980nm diode laser, and compare between diode laser 980nm and diode laser 635nm

### Materials and methods

#### Patient assignment and blinding:

30 PATIENTS. Divided in to 2groups.

Comparison between two groups , First one, By using diode laser 635nm (flat top handpiece)

And other group by using diode laser 980nm (flat top handpiece).

The hand-pieces fixed at distances of 3 mm and 15 mm from the power meter, only the FT profile hand-piece had a constant power output, which was comparable to the contact mode.

Introsion criteria:-patients with Tmds due to stress,medically free, not to resort to self-medication during the study period.

Extrusion criteria:-patients with bruxisms, erosions,medically free,diabetics

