### The clinical procedure:

In all groups, the painful points were determined at each assessment interval. Bilateral muscles including masseter (origin, body, and insertion), temporal (anterior, middle, posterior), tendon of temporal, and insertion of internal pterygoid as well as temporomandibular joints (TMJs) at rest and function were palpated and the painful points were recorded in the patient's folder.

Group 1 (low-level laser therapy): patient received laser treatment with diode laser 635nm with flat top hand piece Applied on the trigger points.

Group 2 (low\_level laser therapy): patient received laser treatment with diode laser 980 nm with flat top hand piece Applied on the trigger points.

The laser was applied two times a week for 5 weeks.(23,18)

Both the patient and the operator wore protective goggles during treatment.

The patients in all groups were asked not to resort to self-medication during the study period.

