### Patient assessment:

The patients were evaluated before treatment ,after laser applications ,at the end of treatment , and 1 month after the laser applications.(18)

Evaluation of the patient is determined by pain intensity, maximum mouth opening(MMO), lateral movements(LM), protrusive movements(PM), pressure pain threshold, electromyography activity and TMJ sounds in patients with TMDS.(1,3,4,5)

At each assessment interval, the amount of mouth opening and the range of protrusive and lateral excursive movements of the jaw were measured and recorded. To measure mouth opening, the patient was asked to open the mouth at both "maximum pain-free" and "maximum possible" conditions.

The vertical interincisal distance was then measured with a digital caliper and recorded in millimeters in patient's folder.

The right and left lateral jaw movement was measured in millimeters by detecting the horizontal distance between the midpoints of the upper and lower central incisors.

A visual analog scale (VAS) was used for calculating pain grade right before our therapy. Patients were asked to describe the degree of discomfort/pain from zero to ten, the pain scale read "no pain" and "the greatest pain possible.

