Statistical Analysis Plan (SAP)

Study Title: Efficacy of Photobiomodulation Therapy Using 980nm Versus 635nm Diode Lasers in the Management of Myofascial Pain Syndrome (LLLT-MPS_sEMG)

ClinicalTrials.gov Identifier (NCT Number): NCT07069764

Document Date: 01 May 2025

Prepared by:

Principal Investigator: [name]

Institution: National Institute Enhanced of Laser Sciences

1. Introduction

This Statistical Analysis Plan (SAP) describes the pre-specified statistical methods and procedures that will be used to analyze data for the clinical trial entitled 'Efficacy of Photobiomodulation Therapy Using 980nm Versus 635nm Diode Lasers in the Management of Myofascial Pain Syndrome (LLLT-MPS_sEMG)'.

2. Study Objectives

Primary Objective: To evaluate the effectiveness of photobiomodulation therapy using diode lasers (980nm vs 635nm) in reducing myofascial pain.

Secondary Objectives: To assess improvements in mandibular function and muscle activity (measured using sEMG).

3. Outcome Measures

Primary Outcome: Change in pain intensity measured by the Visual Analog Scale (VAS) from baseline to post-treatment and follow-up.

Secondary Outcomes:

- Change in Maximum Mouth Opening (MMO) from baseline to post-treatment and follow-up.
- Change in Lateral and Protrusive Movements (LM, PM).
- Change in surface electromyography (sEMG) activity of masseter and temporalis muscles.

4. Statistical Methods

Normality of data distribution will be assessed using the Shapiro-Wilk test.

If data are not normally distributed, non-parametric tests will be applied.

Within-group comparisons across time points (baseline, post-treatment, follow-up) will be analyzed using the Friedman test, followed by post-hoc pairwise comparisons with Bonferroni correction if significant differences are detected.

Between-group comparisons will be conducted using the Mann-Whitney U test on change scores.

Significance will be set at $p < 0.05$.

5. Effect Size Calculations

Effect sizes will be calculated to quantify the magnitude of differences:

- Kendall's W for Friedman test results (within-group changes).
- Rank biserial correlation (r) for Mann-Whitney U test results (between-group comparisons).

6. Handling of Missing Data

If missing data occur, an intention-to-treat (ITT) approach will be applied. Sensitivity analyses may be conducted to evaluate the potential impact of missing data.

7. Interim Analyses

No interim analyses are planned for this study.

8. Software

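### The only named between-group test, Mann-Whitney on change scores, leaves the recorded baseline VAS unadjusted and loses precision with 30 patients; the available text also does not say how patients were assigned or masked.

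*Protocol*

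**What the plan says.** **Analysis.** SAP section 3 defines the primary outcome as change in VAS pain from baseline to post-treatment and to follow-up. Section 4 gives the between-group method: "Between-group comparisons will be conducted using the Mann-Whitney U test on change scores". No covariate is named. The same section says "If data are not normally distributed, non-parametric tests will be applied". That implies a parametric alternative for normal data, but none is named.

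**Baseline data.** The protocol's Patient assessment section shows that a baseline value exists: "The patients were evaluated before treatment", and "A visual analog scale (VAS) was used for calculating pain grade right before our therapy". It also lists assessments after laser applications, at the end of treatment and one month later.

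**Assignment.** The protocol section headed Patient assignment and blinding says "30 PATIENTS. Divided in to 2groups". The rest of that section covers the two lasers, the handpiece and eligibility. The clinical procedure section says what each arm received (for group 2, "patient received laser treatment with diode laser 980 nm") but not how patients came to be in it. The available text gives no sequence generation, concealment, allocation ratio or masking for this trial.

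**Intention to treat.** SAP section 6 says "If missing data occur, an intention-to-treat (ITT) approach will be applied". This concerns missing data and describes no allocation procedure.

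**The concern.** The trial's question is the contrast between 980 nm and 635 nm. Subtracting baseline is not the same as adjusting for it. Whenever the correlation between baseline and later VAS is below 1, the change score over-corrects, and part of the baseline noise enters the comparison. With 30 patients and no stated sample-size justification, that loss of precision matters, and the variable that would recover it is already collected.

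The unstated assignment method matters because it decides what either analysis means. Under random allocation the choice between them is one of efficiency. If patients with more recorded pain tended to go to one arm, regression to the mean would give the arms different changes with no wavelength effect at all. If the arms instead differed in some lasting characteristic, the baseline-adjusted analysis would be the misleading one.

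**Working it through.** **Inputs.** From the documents: 30 patients, two groups, significance at 0.05, Mann-Whitney on change. Assumed, because the documents do not give them: 15 per arm, a two-sided test, normal VAS with equal SDs (set to 1) at both times, correlation ρ of 0.3, 0.5 or 0.7, and true effects of 0.5 or 1 SD. The figure of 30 has no stated effect, SD or power behind it, so there is no calculation in the plan to reproduce.

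**Step 1: variance under random allocation.**
- Change score: 2(1 − ρ) = 1.40, 1.00, 0.60.
- ANCOVA residual: 1 − ρ² = 0.91, 0.75, 0.51.
- Ratio: 2(1 − ρ)/(1 − ρ²) = 2/(1 + ρ) = 1.54, 1.33, 1.18.

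**Step 2: power under random allocation.** Simulation with 40,000 trials per cell (10,000 for rank ANCOVA). The exact Mann-Whitney test rejects at U ≤ 64, which has true size 0.045. ANCOVA uses a t-test on 27 degrees of freedom.

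| True effect | Analysis | ρ = 0.3 | ρ = 0.5 | ρ = 0.7 |
|---|---|---|---|---|
| 1 SD | Mann-Whitney on change | 57% | 72% | 91% |
| 1 SD | t-test on change | 61% | 75% | 93% |
| 1 SD | ANCOVA | 78% | 85% | 95% |
| 1 SD | Rank ANCOVA | 75% | 82% | 92% |
| 0.5 SD | Mann-Whitney on change | 18% | 24% | 37% |
| 0.5 SD | ANCOVA | 28% | 32% | 45% |

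The t-test row separates the two sources of loss. At 1 SD and ρ = 0.5, ranks and the conservative exact size cost about 3 points (75% to 72%). The missing adjustment costs about 10 (85% to 75%).

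**Step 3: validity under random allocation.** With no true effect, Mann-Whitney on change rejects in about 4.5% of trials and ANCOVA in about 5%. Neither is biased.

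**Step 4: what non-random assignment could do (hypothetical).** No true effect, ρ = 0.5, and gaps between arms of 0.5, 1.0 and 1.5 SD:
- Assignment on recorded baseline VAS: the expected change-score difference is (1 − ρ) × gap, that is 0.25, 0.50 and 0.75 SD. Mann-Whitney on change falsely rejects in 9%, 24% and 47%; ANCOVA stays near 5%.
- Arms differing in a stable characteristic: Mann-Whitney on change holds at 4–5%; ANCOVA falsely rejects in 11%, 27% and 44%.

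For scale, the standard error of the baseline difference under randomisation is √(2/15) = 0.37 SD. A chance gap above 0.5 SD therefore occurs in about 17% of randomised trials, and one above 1.0 SD in about 0.6%. The larger gaps would need real selection.

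**The case against.** The strongest defence is that the planned test is legitimate. If allocation was random, Mann-Whitney on change keeps its type I error and directly tests the outcome the SAP names, which is a change in pain. That stands: under randomisation, adjusting for baseline improves the plan but does not repair an invalid test.

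A reader might infer from the word for dividing patients that allocation was left to the operator, or followed pain severity. The documents do not support that. The protocol's literature review uses similar wording, "were recruited and divided into two groups", for a cited sham-controlled laser trial whose title in the reference list says it was randomised and blinded. The opening part of the protocol was also removed before review and may describe the design. The intention-to-treat wording points weakly the other way. So the bias scenarios in step 4 show only what is at stake if the method is not stated.

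A reader might also take ANCOVA as a cure for unknown allocation. It is not: step 4 shows that it fails when the arms differ in a stable way.

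The size of the gain is fairly contested too. An effect of 1 SD between two active lasers is unsupported by the documents, and at 0.5 SD neither analysis has useful power. Part of the gap comes from ranks and the exact test's size. At ρ = 0.7 rank ANCOVA barely gains (92% against 91%). Finally, the protocol describes treatment and assessment in the past tense, so assignment may already be over.

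**Conclusion.** The point holds as one about precision and missing detail; no bias has been shown. SAP section 4 leaves a recorded baseline unused. Under random allocation this inflates the variance of the comparison by a factor of 1.18 to 1.54 for correlations from 0.7 down to 0.3. At 1 SD it is part of a power gap of about 5 to 21 points against ANCOVA, largest where the correlation is low. These sizes rest on assumed arm sizes, SDs, correlation and effect, and on normal data.

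Separately, the section meant to describe assignment and blinding gives neither procedure. This does not show a non-randomised trial. It does leave a reader unable to judge which analysis of the 980 nm versus 635 nm contrast can be trusted. It should be fixed, and the change is cheap.

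**What to change.** 1. **State the facts first.** In the protocol's Patient assignment and blinding section and in the SAP, say how the 30 patients were or will be assigned, in what ratio, and who was masked to wavelength. If assignment is still to come, use a computer-generated 1:1 list, concealed until baseline measurements are recorded.
2. **If allocation is or was random,** replace the primary between-group comparison with an ANCOVA of VAS at one named time point on baseline VAS and arm. The end of treatment could be primary, with the one-month follow-up secondary. Fix the method in advance, either ANCOVA with a permutation or robust p-value or rank ANCOVA, and do not let a normality test choose it. Keep Mann-Whitney on change as a sensitivity analysis.
3. **If assignment was not random,** label the study non-randomised in the SAP and report, limit the causal conclusion, and report both the change-score and the baseline-adjusted analyses. Say which form of selection each one handles.

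The analysis change needs no extra patients and uses the baseline VAS already planned. It costs one model specification and a little more analysis work. A concealed list, if still possible, adds some organisation, and the documents do not describe the staffing for it. The two analyses may disagree, and the report must then say so.

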#### Pico:-

Population:patients with myofacial pain.

Intervention:grouo1,using diode laser 635nm

Comparison:group2,using diode laser 980nm

Outcome:primary outcome:relief pain

Secondary outcome: maximum mouth opening(MMO), lateral movements(LM), protrusive movements(PM).

### The clinical procedure:

In all groups, the painful points were determined at each assessment interval. Bilateral muscles including masseter (origin, body, and insertion), temporal (anterior, middle, posterior), tendon of temporal, and insertion of internal pterygoid as well as temporomandibular joints (TMJs) at rest and function were palpated and the painful points were recorded in the patient's folder.

Group 1 (low-level laser therapy): patient received laser treatment with diode laser 635nm with flat top hand piece Applied on the trigger points.

Group 2 (low\_level laser therapy): patient received laser treatment with diode laser 980 nm with flat top hand piece Applied on the trigger points.

The laser was applied two times a week for 5 weeks.(23,18)

Both the patient and the operator wore protective goggles during treatment.

The patients in all groups were asked not to resort to self-medication during the study period.

### Patient assessment:

The patients were evaluated before treatment ,after laser applications ,at the end of treatment , and 1 month after the laser applications.(18)

Evaluation of the patient is determined by pain intensity, maximum mouth opening(MMO), lateral movements(LM), protrusive movements(PM), pressure pain threshold, electromyography activity and TMJ sounds in patients with TMDS.(1,3,4,5)

At each assessment interval, the amount of mouth opening and the range of protrusive and lateral excursive movements of the jaw were measured and recorded. To measure mouth opening, the patient was asked to open the mouth at both "maximum pain-free" and "maximum possible" conditions.

The vertical interincisal distance was then measured with a digital caliper and recorded in millimeters in patient's folder.

The right and left lateral jaw movement was measured in millimeters by detecting the horizontal distance between the midpoints of the upper and lower central incisors.

A visual analog scale (VAS) was used for calculating pain grade right before our therapy. Patients were asked to describe the degree of discomfort/pain from zero to ten, the pain scale read "no pain" and "the greatest pain possible.

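### Neither the protocol nor the SAP provides for recording or reporting unwanted effects, so two active lasers would be compared on efficacy measures alone

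*Protocol*

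**What the plan says.** **What is measured.** The protocol, under Patient assessment, states: "Evaluation of the patient is determined by pain intensity, maximum mouth opening(MMO), lateral movements(LM), protrusive movements(PM), pressure pain threshold, electromyography activity and TMJ sounds". The clinical procedure section adds that painful points on palpation are re-determined at each assessment. SAP section 3 has VAS change as the primary outcome. Its secondary outcomes are mouth opening, lateral and protrusive movement, and surface EMG.

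**When.** On treatment: "The laser was applied two times a week for 5 weeks". On assessment: "The patients were evaluated before treatment ,after laser applications ,at the end of treatment , and 1 month after the laser applications".

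**How many.** "30 PATIENTS. Divided in to 2groups". The allocation ratio is not given.

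**How it is analysed.** SAP sections 4 and 5 plan Friedman tests within groups and Mann-Whitney tests on change scores between groups, with Kendall's W and the rank-biserial correlation as effect sizes. Section 6 invokes intention to treat if data are missing. It does not ask why a session or patient was lost. The SAP has no safety outcome and no safety section.

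**What is said about safety.** There are three remarks. The clinical procedure section says "Both the patient and the operator wore protective goggles during treatment". The literature review summarises a trial of LED against laser with the comment that "the biosafety and lower cost of the LED light device compared to the LASER should also be considered". It also summarises a 940 nm trial as free of systemic side effects.

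**The concern.** Both arms receive an active laser, so the practical product of the trial is a preference between two wavelengths. A preference normally weighs benefit against unwanted effects, and this plan collects only the first.

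Two consequences follow. A local skin or eye effect, or a pain flare that settles between assessments, has no planned place in the record. And if the report is silent on harm, a reader may take this to mean that nothing happened, when the plan made no provision for looking. A patient who stopped because of a reaction would appear only as missing data, since SAP section 6 does not call for the reason.

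**Working it through.** The plan states no safety figure, so there is none to reproduce. The check is a comparison of sections, followed by arithmetic on what recording could deliver.

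**1. Coverage of possible unwanted effects**

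| Type of effect | Planned record? | Planned report? |
|---|---|---|
| Pain worse at an assessment | Yes (VAS, painful points) | Only within rank tests on change |
| Mouth opening or jaw movement worse at an assessment | Yes | Only within rank tests on change |
| Pain flare between assessments | None stated | None |
| Skin effect | None stated | None |
| Eye effect | None stated | None |
| Reason for a missed session or withdrawal | None stated | None |

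The assessment labelled as after laser applications might mean after every session. Even on that reading, the listed items include nothing on skin or eyes.

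**2. Exposure**

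2 sessions per week × 5 weeks = 10 sessions per patient. With full attendance, 30 × 10 = 300 sessions.

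**3. What a recorded zero would support**

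With 0 events in n patients, the exact upper limit is 1 − 0.025^(1/n) for a two-sided 95% interval and 1 − 0.05^(1/n) for a one-sided 95% bound. The split of the 30 patients is not stated. I assume 15 per arm and show 10 and 20 as a range.

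| n in arm | Two-sided 95% upper limit | One-sided 95% bound |
|---|---|---|
| 10 | 30.8% | 25.9% |
| 15 | 21.8% | 18.1% |
| 20 | 16.8% | 13.9% |

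If nothing is recorded, no limit can be stated.

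**4. Chance of seeing at least one event in an arm of 15**

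This is 1 − (1 − p)^15, where the true per-patient rate p is an assumption: 14% at p = 1%, 54% at p = 5%, 79% at p = 10%.

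**5. Why a significance test would not help**

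At 15 versus 15, Fisher's exact test gives p = 0.0996 for 0 versus 4 patients with events and p = 0.042 for 0 versus 5. Its exact power is 8% for assumed true rates of 5% versus 20%, and 52% for 5% versus 40%. The data would support counts and intervals, not a comparative safety test.

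**6. Whether the planned outputs show individual worsening**

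Take invented change scores. In arm A, 11 patients improve by 3 points and 4 improve by 4 (mean change −49/15 = −3.27). In arm B, 12 improve by 5 and 3 worsen by 2 (mean change −54/15 = −3.60). Mann-Whitney favours B (U = 180 of 225, p = 0.003, |r| = 0.60), although 3 of 15 worsened in B and none in A. The planned statistics would not reveal this, but a simple count would.

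**The case against.** **The documents give no positive sign of a harm difference.** This stands. A reader might infer from the goggles that the protocol identifies an eye hazard, but it names none. A reader might also take the biosafety comment as a warning about these lasers. It contrasts LED with laser in a cited study, and both arms here are lasers, so it says nothing about 635 nm against 980 nm. The 940 nm summary points towards safety, though only for systemic effects.

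**The comparison is not on pain alone.** This also stands. Mouth opening, jaw movement and surface EMG are compared too. The accurate statement is that only efficacy and function measures are compared.

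**Worsening is already captured.** In part. Pain or opening that is worse at an assessment is measured, so that gap is one of reporting. Skin and eye effects and transient flares remain unrecorded.

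**Counting patients who worsened is a preference, not a correction.** Largely right. A rule of any change beyond baseline has no margin for measurement error. With no untreated or sham arm, such counts cannot separate a laser effect from natural fluctuation.

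**Recording events would not settle comparative safety.** Correct, as the power figures show. The benefit is descriptive.

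**It may be too late.** Possibly. Treatment and assessment are described largely in the past tense, and SAP section 9 places approval only before database lock and analysis. The fix has to cover both situations.

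**Something may lie in pages not seen.** The consent pages and the opening part of the protocol were not in the text examined, so the statement is limited to the visible sections.

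**Conclusion.** The gap is real and limited in scope. In the visible text, no session or visit has a planned record of unwanted effects, and the SAP has no place to report them. A trial run as written could therefore choose between two active lasers with no harm information beyond whatever shows up in the efficacy measures.

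It would go too far to conclude that one wavelength is more harmful. That is a possibility the plan cannot examine, not something the documents show.

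The gain from repair is modest. Assuming 15 per arm, zero recorded events would still be compatible with a per-patient rate up to 21.8% (two-sided 95% limit; 18.1% as a one-sided bound). That is a weak statement, but it is an honest one, and without recording there is none. The change is worth making because it bears on patient safety and costs little.

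**What to change.** **If sessions remain.** At each remaining session and at the 1-month visit, record one standard question on unwanted effects (skin, eye, increased pain). Record the reason for any missed session or withdrawal. Add to the SAP a descriptive table by arm of the number of patients with any event, with exact two-sided 95% confidence intervals and no significance test. If some sessions have already passed, state from which point recording began.

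**If treatment is complete.** State in the report that unwanted effects were not systematically sought and that no conclusion on comparative safety can be drawn.

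**Optional in either case.** Give counts by arm of patients whose VAS or mouth opening is worse than at baseline, from data already planned. Label them descriptive, and say that without an untreated arm they are not evidence of laser harm.

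**Cost.** One short item on a form at visits that already take place, and one table. The drawback is that any safety statement will carry wide limits.

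### Averaging three readings per visit would be a cheap gain in precision: the plan describes one VAS rating and one value per jaw movement, then analyses change scores in 30 patients

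*Protocol*

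**What the plan says.** The protocol's Patient assessment section describes the pain measure in two sentences: "A visual analog scale (VAS) was used for calculating pain grade right before our therapy", and "Patients were asked to describe the degree of discomfort/pain from zero to ten". No second rating, diary or averaging rule appears.

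For the jaw, the same section says that at each assessment "the amount of mouth opening and the range of protrusive and lateral excursive movements of the jaw were measured and recorded". For mouth opening, "the patient was asked to open the mouth at both 'maximum pain-free' and 'maximum possible' conditions", and "The vertical interincisal distance was then measured with a digital caliper and recorded in millimeters". Lateral movement is measured to the right and to the left. The two opening conditions and the two sides are different quantities, so they are not repeats of one another. No number of attempts is given, and no rule for taking the first, the best or the mean.

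SAP section 3 makes the primary outcome "Change in pain intensity measured by the Visual Analog Scale (VAS) from baseline to post-treatment and follow-up", and defines the jaw outcomes as changes too. SAP section 4 states: "Between-group comparisons will be conducted using the Mann-Whitney U test on change scores". There is no baseline adjustment. On size, the protocol (Patient assignment and blinding) has only "30 PATIENTS. Divided in to 2groups". Neither document gives a power calculation, effect size, SD or reliability.

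**The concern.** A change score is the difference of two readings. If each carries independent error, the change carries twice the error variance of one reading. Pain attributed to stress, which is the protocol's entry criterion, can vary from day to day. A jaw movement at maximal effort can vary between attempts. Averaging repeats removes part of this noise without enrolling anyone.

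What is at stake is precision. Both arms are active lasers, so the difference between wavelengths could be small, and a trial of this size has little precision to spare. The primary VAS comparison and the mouth-opening, lateral and protrusive comparisons are all affected.

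**Working it through.** **The plan's own figure.** The total of 30 cannot be reproduced, because no inputs are given for it. Assuming 15 per arm, two-sided alpha 0.05, and Mann-Whitney efficiency of 0.955 relative to the t-test under normality, the difference detectable with 80% power is (1.960 + 0.842) × √(2 / (15 × 0.955)) ≈ 1.05 SD of the change score.

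**Formula.** Let τ be the SD of true change, σ the SD of reading-to-reading (or day-to-day) error, and r the correlation of errors among repeats at one visit. Then Var(change) = τ² + 2σ²g, with g = 1 for one reading and g = (1 + 2r)/3 for the mean of three. All values of τ, σ and r below are assumptions.

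**VAS, τ = 1.5 points**

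| σ | r | one reading | mean of three | cut |
|---|---|---|---|---|
| 0.5 | 0.3 | 2.25 + 0.50 = 2.75 | 2.25 + 0.50 × 0.533 = 2.52 | 8% |
| 0.5 | 0.5 | 2.75 | 2.25 + 0.50 × 0.667 = 2.58 | 6% |
| 1.5 | 0.3 | 2.25 + 4.50 = 6.75 | 2.25 + 4.50 × 0.533 = 4.65 | 31% |
| 1.5 | 0.5 | 6.75 | 2.25 + 4.50 × 0.667 = 5.25 | 22% |
| 2.0 | 0.3 | 2.25 + 8.00 = 10.25 | 2.25 + 8.00 × 0.533 = 6.52 | 36% |
| 2.0 | 0.5 | 10.25 | 2.25 + 8.00 × 0.667 = 7.58 | 26% |

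Simulated Mann-Whitney power for an assumed 2-point difference, 15 per arm:
- σ = 1.5: from about 0.49 to about 0.65 (r = 0.3) or about 0.60 (r = 0.5; simulation runs gave 0.59 to 0.61).
- σ = 0.5, r = 0.3: from about 0.86–0.87 to 0.89–0.90, a gain of roughly 3 points.

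**Maximum mouth opening, τ = 4 mm**
- σ = 1, r = 0: 16 + 2 = 18 falls to 16 + 0.67 = 16.67, a cut of 7%.
- σ = 2, r = 0: 16 + 8 = 24 falls to 16 + 2.67 = 18.67, a cut of 22%.
- σ = 3, r = 0: 16 + 18 = 34 falls to 16 + 6 = 22, a cut of 35%.
- σ = 2, r = 0.5: 24 falls to 16 + 5.33 = 21.33, a cut of 11%.

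**Cross-check in other terms.** Set the single-reading SD to 1, the between-visit correlation to ρ = 0.5 and the reliability to R. With k readings, Var(change) = 2(1 − ρ) − 2(1 − R)(1 − 1/k). For k = 3 this falls from 1 to 0.933 at R = 0.95, and to 0.60 at R = 0.70. For a true difference of 1.0 single-reading SD, simulated Mann-Whitney power rises from about 0.72 to 0.75 and 0.90 respectively. The direction is the same, and the size again depends on an unknown.

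**Baseline adjustment.** With ρ = 0.5 and one reading per visit, the variance is 2(1 − 0.5) = 1 for change and 1 − 0.5² = 0.75 after adjustment. For a difference of 1.0 SD, normal-theory power is about 0.782 and 0.885. Averaging still adds to this. In the central VAS case, assume also a true-baseline SD of 1.5, unrelated to true change. The adjusted variance is then 6.75 − 2.25²/4.50 = 5.63 with one reading, and 5.70 − 2.25²/3.45 = 4.23 with three, a further cut of 25%.

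**The case against.** The strongest reply is that one rating per visit is neither a contradiction nor an error, and that the gain is of unknown size. That stands. With reliable readings the gain is a few points of power.

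Second, a multi-day VAS average can do harm. The protocol places the rating just before therapy. If treatment starts at that visit, a mark made on a later day is a post-laser rating averaged into baseline. That would distort change in both arms, and unequally if one wavelength acts faster. Averaging also alters what is measured, from pain at one moment to a three-day mean. Both points stand, and they are why the VAS step is optional and tied to conditions.

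Third, baseline adjustment is free. True, but the later reading stays noisy, so the two steps add together.

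Fourth, single readings are inferred from the wording and from silence, and repeats may simply have gone unmentioned. In that case the plan should still state their number and the averaging rule, so that first, best or mean is not chosen after the data are seen. The protocol's past tense and the SAP's reference to database lock might suggest that it is too late to add readings, but the documents do not show that data collection is complete.

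A reader might also infer that, with only 30 patients, this noise must be a large share of the variance. That does not follow. The share does not depend on sample size, and under the assumed inputs it runs from 18% (0.50/2.75) to 78% (8.00/10.25) for VAS.

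**Conclusion.** This is a cheap improvement, not an error. As written, single-reading error enters each change score at both visits and costs some power. Averaging three readings would cut change-score variance by about 6% to 36% for VAS (τ = 1.5, σ = 0.5 to 2.0, r = 0.3 to 0.5). For mouth opening the cut is about 7% to 35% with independent errors (τ = 4 mm, σ = 1 to 3 mm), and the central 22% halves to 11% if errors correlate at 0.5. Every one of these inputs is assumed.

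It is tempting to turn the central VAS case into a statement that averaging is worth about 44 patients (30 × 6.75/4.65 = 43.5). The documents do not support that as a finding, since it is one point in a wide range. Nor do they support a claim of bias: extra noise that is alike in the two arms widens the comparison without shifting it.

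**What to change.** **Main change, jaw movements.** In the protocol's Patient assessment section, take three readings of each jaw movement, side and condition at each assessment. In SAP section 3, define MMO, LM and PM at each visit as the mean of the three, kept separate by side and condition. Cost: about two minutes of measuring time per visit.

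**Optional change, VAS.** At the SAP's three time points, collect the same 0–10 rating on three consecutive days, with the clinic rating as one of the three, and average those available. Four conditions apply:
- All baseline ratings are completed before the first laser session.
- All end-of-treatment ratings come after the last session.
- The days are fixed in advance and are identical in both arms.
- The SAP states that the outcome is then a three-day average, and keeps the single clinic rating as a sensitivity analysis.

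The protocol's additional assessment after laser applications is not one of the SAP's analysed time points, so it keeps its single rating. Cost: a card with two extra marks per time point. Some cards will be incomplete, and the clinic rating then stands alone.

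**Complementary step.** Consider a baseline-adjusted between-group analysis in SAP section 4. It uses the existing readings and needs no further measurement.
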